10.4 Publication of study protocol and results

Novartis assures that the key design elements of this protocol will be posted in a publicly accessible database such as clinicaltrials.gov. In addition, upon study completion and finalization of the study report the results of this study will be either submitted for publication and/or posted in a publicly accessible database of clinical study results.

[figure not shown]
11 Protocol adherence

This protocol defines the study objectives, the study procedures and the data to be collected on study participants. Additional assessments required to ensure safety of patients should be administered as deemed necessary on a case by case basis. Under no circumstances should an Investigator collect additional data or conduct any additional procedures for any research related purpose involving any study drugs.

Investigators ascertain they will apply due diligence to avoid protocol deviations. If an Investigator feels a protocol deviation would improve the conduct of the study this must be considered a protocol amendment, and unless such an amendment is agreed upon by Novartis and approved by the IRB/IEC, it cannot be implemented. All significant protocol deviations will be recorded and reported in the Clinical Study Report.

No specific action is pre-defined within this protocol to respond to specific abnormal laboratory values, as it will be decided by the Investigator/qualified site staff whether and which specific action needs to be taken to respond to any abnormal values, taking into account the overall status of the patient. For additional information please refer to the lab manual.

Liver function and related variables

ALT (SGPT):	> 3 x upper limit of normal (ULN)
AST (SGOT):	> 3 x ULN
Total bilirubin:	> 1.5 x ULN
Alkaline phosphatase:	> 2 x ULN

Renal function and electrolyte variables

Creatinine (serum):	> 1.5 x ULN
---------------------	-------------

Hematology variables

Hemoglobin:	≥ 20 g/dL decrease from Baseline
Platelet count:	< lower limit of normal (LLN)
White blood cell count:	< 0.8 x LLN
Neutrophils:	< 0.9 x LLN
Eosinophils:	> 1.1 x ULN
Lymphocytes:	> 1.1 x ULN

Urinalysis variable

Protein urine dipstick:	+++ (* ++ is ≥ 100 mg/dL)
-------------------------	--------------------------------

The content of this SAP is based on the final version of protocol CAIN457A3401 (release date 21-Oct-2015). All decisions regarding final analysis, as defined in the SAP document, have been made prior to database lock and unblinding of the study data.

1.1 Study design

The study is an open-label, prospective, non-randomized but stratified multicenter study to evaluate clear skin effect on health-related quality of life outcomes at 16 and 52 weeks in patients with moderate to severe plaque psoriasis treated with secukinumab 300 mg s.c. with or without previous exposure to systemic therapy.

A total of 1615 patients will be enrolled into the study. Eligible patients will be categorized at baseline according to previous exposure to treatment in one of the following 3 subpopulations:

- **Subpopulation A:** Patients who are **naïve to any systemic treatment**, e.g. patients failing or intolerant to previous topical treatment, including narrow band UVB, but never exposed to any systemic treatment, with or without contraindications to the use of conventional systemic treatment and in a need of a first systemic treatment.
- **Subpopulation B:** Patients who have been **previously exposed to at least one conventional systemic therapy**; either because of failure or intolerance to their previous conventional systemic treatment, they are in a need of a first biologic systemic treatment;
- **Subpopulation C:** Patients who have been **previously exposed to at least one biologic systemic therapy**; either because of failure or intolerance to their previous biologic systemic treatment, they are in a need of a different biologic systemic treatment.

The primary endpoint of this study is the proportion of patients achieving a Dermatology Life Quality Index (DLQI) 0/1 response at Week 16 in the 3 subpopulations and in the overall study population.

One interim analysis will be performed after LPFT. The purpose of the interim analysis is to describe the self-reported baseline characteristics and health-related Quality of Life (HR-QoL) of patients prior to treatment.

[figure not shown]
1.2 Study objectives and endpoints

Primary objective:

- To assess the proportion of patients achieving a DLQI 0/1 response at Week 16 in the 3 subpopulations and in the overall study population.

Secondary objectives:

- To assess the proportion of patients achieving a DLQI 0/1 response at Week 52 in the 3 subpopulations and in the overall study population.
 - To assess the effects of treatment with secukinumab 300 mg with respect to changes in EuroQoL 5-Dimension Health Questionnaire[®] (EQ-5D), Health Assessment Questionnaire[®]-Disability Index (HAQ-DI), Numeric Rating Scale (NRS), Treatment Satisfaction Questionnaire for Medication (TSQM) and Patient Benefit Index (PBI) response over time up to Week 16 and Week 52 compared to baseline in the 3 subpopulations and in the overall study population.
 - To assess the proportion of patients achieving Psoriasis Area and Severity Index (PASI) 50, PASI 75, PASI 90, PASI 100 and Novartis Investigator's Global Assessment modified 2011 (IGA mod 2011) 0/1 responses at Week 16 and Week 52 in the 3 subpopulations and in the overall study population.
 - To assess the proportion of patients with DLQI scores 2-5, 6-10, 11-20, 21-30 at Week 16 and Week 52 compared to baseline in the 3 subpopulations and in the overall study population.
 - To assess the overall safety and tolerability of treatment with secukinumab 300 mg in the 3 subpopulations and in the overall study population.
- 

2 Statistical methods

Statistical methods are based on study protocol section 9 with more details given in this SAP.

2.1 Data analysis general information

The statistical analysis of the study (including the interim analysis) will be performed by [REDACTED], a designated Contract Research Organization (CRO).

SAS version 9.3 or later will be used to perform all data analyses and to generate tables, figures and listings.

Qualitative data (e.g., gender, race, etc.) will be summarized by means of contingency tables; a missing category will be included as applicable. Percentages will be calculated using the number of patients in the relevant population or subgroup as the denominator.

Quantitative data (e.g., age, body weight, etc.) will be summarized by appropriate descriptive statistics, i.e., n, mean, standard deviation (SD), first quartile (Q1), median, third quartile (Q3), minimum, and maximum.

Data from all study centers will be pooled for the analysis.

2.1.1 General definitions

Investigational drug and study treatment

The same study drug will be given to all patients recruited in the 3 subpopulations: secukinumab/AIN457 300 mg s.c. No reference therapy will be given.

Date of first and last administration of study drug

The date/time of first administration of secukinumab is defined as the first date/time of administration as per Study drug administration eCRF. The date/time of last administration of secukinumab is defined as the last date/time when a dose is administered as per Study drug administration eCRF.

Study day

The study day, describes the day of the event or assessment date, relative to the reference start date which is the date of first administration of secukinumab.

The study day is defined as:

- The date of the event (visit date, onset date of an event, assessment date etc.) – reference start date + 1 if event is on or after the reference start date;
- The date of the event (visit date, onset date of an event, assessment date etc.) – reference start date if event precedes the reference start date.

Baseline

For safety and efficacy evaluations, the last available assessment before the first administration of secukinumab is defined as “baseline” assessment. If patients have no value prior to first administration of secukinumab the baseline result will be missing.

Post-baseline

For safety and efficacy evaluations all assessments after the first administration of secukinumab are defined as “post-baseline” assessment.

Change and percent change from baseline for continuous parameter.

Change from baseline and percent change from baseline will only be summarized for subjects with both baseline and post-baseline values and will be calculated as:

change from baseline = post-baseline value – baseline value

percent change from baseline = $100 * \text{change from baseline} / \text{baseline value}$

Study periods and date of last contact

The overall observation period will be divided into three mutually exclusive segments:

- A screening phase of 4 weeks
- A treatment phase 1 starting with first dose of study drug at Visit 2 and covering the first 16 weeks of treatment.
- A treatment phase 2 starting with the dosing at Visit 9 (Week 16) and lasting until end of the study, Visit 14 (Week 52).

According to the protocol for patients not achieving a PASI 50 response at the Week 16, i.e. at the end of treatment phase 1, considerations should be given to discontinuing study drug. Thus patients can complete treatment phase 1 without entering treatment phase 2.

For patients entering treatment phase 2, the treatment phase 2 date of discontinuation/study phase completion will be used as the date of last contact. For subjects not entering treatment phase 2, the treatment phase 1 date of discontinuation/study phase completion will be used.

Visit windows

Visit-windows will be used for the data that is summarized by visit; they are based on the study evaluation schedule and comprise a set of days around the nominal visit day. For any assessment, there are the protocol defined scheduled visits around which visit windows were created to cover the complete range of days within the study. When visit windows are used, all visits will be re-aligned, i.e., they will be mapped into one of the visit windows.

In general, if two consecutive visits V_t and V_s are x days apart, the upper limit of the visit window for V_t will be $V_t+x/2$ and the lower limit for the visit V_s will be $V_s-x/2$ (if x is even, the lower limit for V_s will be $V_s-x/2+1$, and the upper limit for V_t will be $V_t+x/2$). The algorithm needs to ensure that visit windows are not overlapping and that there are no gaps, such that each assessment can be uniquely allocated to one visit window.

The visit windows are shown in Table 2-1.

Table 2-1: Visit windows

Analysis Week visit	Sched. Day	Visit window – assessments ^a scheduled at all visits	Visit window - assessments ^b scheduled at visits 2, 6, 8, 9, 10, 11, 12, 13 and 14	Visit window - assessments ^c scheduled at visits 2, 6, 8, 9, 11, 12, 13 and 14	Visit window – assessments ^e scheduled at visits 2, 9 and 13 and 14	Visit window – assessments ^f scheduled at visits 2, 9 and 14	
Base-line	BL	1	Day -99 to Day 1 (pre-dose)	Day -99 to Day 1 (pre-dose)	Day -99 to Day 1 (pre-dose)	Day -99 to Day 1 (pre-dose)	Day -99 to Day 1 (pre-dose)
3	1	8	Day 1 (post dose) – Day 11				
4	2	15	Day 12 – Day 18				
5	3	22	Day 19 – Day 25				
6	4	29	Day 26 – Day 43	Day 1 (post dose) – Day 57	Day 1 (post dose) – Day 57		
7	8	57	Day 44 – Day 71				
8	12	85	Day 72 – Day 99	Day 58 – Day 99	Day 58 – Day 99		
9	16	113	Day 100 – Day 127	Day 100 – Day 127	Day 100 – Day 141	Day 1 (post dose) – Day 225	Day 1 (post dose) – Day 239
10	20	141	Day 128 – Day 155	Day 128 – Day 155			
11	24	169	Day 156 – Day 211	Day 156 – Day 211	Day 142 – Day 211		
12	36	253	Day 212 – Day 295	Day 212 – Day 295	Day 212 – Day 295		
13	48	337	Day 296 – Day 351	Day 296 – Day 351	Day 296 – Day 351	Day 226 – Day 351	
14	52	365	Day 352 – Day 379	Day 352 – Day 379	Day 352 – Day 379	Day 352 – Day 379	Day 240 – Day 379

a: Body Surface Area (BSA), PASI, IGA mod 2011

b: laboratory sampling (Hematology, Chemistry and Urinalysis) and vital signs

c: NRS, DLQI, EQ-5D, HAQ-DI, TSQM, PBI

e: Fasting laboratory

f: (weight, waist and hip circumference)

In the case of major deviations from the visit schedule, or due to unscheduled visits, several assessments of a subject may fall in a particular visit window (either scheduled or unscheduled). In this case, the following rules are applied to select one value “representing”

the subject in summary statistics in a visit window. For baseline assessment definition see Section for Baseline above. For post-baseline visit windows the following applies:

- for *quantitative variables and qualitative efficacy variables*, the closest to the actual visit is chosen (if two assessments have the same distance, then the earlier one will be chosen);
- for *qualitative safety variables*, the worst record is selected. It is noted that in the analyses performed, worst case is always well defined (e.g., for urine dipstick values “+” and “++”, the worst case is defined as “++”),
- in case *qualitative variables are based on quantitative variables*, e.g. PASI 75 response, the visit will be assigned to the quantitative variable, and this visit will be used for the derived qualitative variable.

For the analysis of assessments done at Screening, the Screening visit will be analyzed as reported on the eCRF.

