The date of the new informed consent signature must be entered on the appropriate CRF page. Informed consent for a screened or rescreened patient must be obtained prior to performing any study-related assessment or collecting any data for the Screening Visit. For rescreening, all Screening assessments must be performed in accordance with the protocol, except for the TB work up, if applicable, if performed not more than 12 weeks prior to Day 1 (Baseline). If the date of the TB work-up is less than 12 weeks from Baseline then the TB work-up does not have to be repeated; however, the patient must repeat the QFT analyzed by the central laboratory.

During the study, patients may be seen at an unscheduled visit, e.g. if they experience deterioration of psoriasis or suspected AEs. During these unscheduled visits, study drug will NOT be administered.

Patients should be seen for all visits on the designated day or as closely as possible to the original planned visit schedule (recommended visit windows are in [Table 6-1](#)) calculated starting from Baseline. Every effort should be made to respect the timeframe for all visits.

Recommended visit windows

Treatment periods:

- ± 2 days for Visits 2, 3, 4, 5 and 9 (Baseline, Week 1, 2, 3, 4 and 16) in Treatment Period 1;
- ± 2 days for all study drug home administrations
- ± 5 days for all other study visits
- Visit 1 and Visit 2 must not be conducted on the same day and all relevant information for Visit 2 must be available before treating the patient. It is recommended that the Screening period does not exceed 4 weeks.

Patients who discontinue study drug prematurely for any reason (other than withdrawal of informed consent) before the end of the main treatment period will enter a 4 weeks post treatment follow-up period, unless the patient withdraws his/her informed consent, in which case an end-of study visit should be performed, if agreeable by the patient.

[figure not shown]

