Other medical history	X															
Prior and concomitant medications	X	X	X	X	X	X	X	X	X	X	X	X	X	X	X	
Physical examination	S	S	S	S	S	S	S	S	S	S	S	S	S	S	S	
Height	X														X	
Weight	X	X							X					X	X	
Vital signs	X	X				X	X	X	X	X	X	X	X	X	X	

[figure not shown]
		Treatment Period 1							Treatment Period 2							
Period	Scr							EOT1					EOT2	Uns ^d	Comments	
Visit	1	2	3	4	5	6	7	8	9 ^{a, b}	10	11	12	13	14 ^c		
Week	-4 to BL	BL	1	2	3	4	8	12	16	20	24	36	48	52		
Recommended visit window (days)		±2	±2	±2	±2	±5	±5	±5	±2	±5	±5	±5	±5	±5		
Waist and hip circumference	X	X							X					X		
Laboratory sampling: safety panel (clinical chemistry, hematology, urine dipstick)	X	X				X		X	X	X	X	X	X	X	X	Samples will be shipped to the central laboratory for analysis. Urine dipstick to be used locally
Fasting labs: glucose, lipid panel, hsCRP, HbA1C		X							X				X	X		
QuantiFERON [®] TB-Gold in-tube test	X														X	
Serum pregnancy test	X														X	Only for females of child-bearing potential.
Urine pregnancy test (local)		X				X		X	X			X		X	X	In the event of a positive urine pregnancy test, study drug must be withheld and a serum pregnancy test performed at the same visit. A urine pregnancy test is not required for a woman who is sterile or who is post-menopausal.

		Treatment Period 1							Treatment Period 2						
Period	Scr							EOT1					EOT2	Uns ^d	Comments
Visit	1	2	3	4	5	6	7	8	9 ^{a, b}	10	11	12	13	14 ^c	
Week	-4 to BL	BL	1	2	3	4	8	12	16	20	24	36	48	52	
Recommended visit window (days)		±2	±2	±2	±2	±5	±5	±5	±2	±5	±5	±5	±5	±5	
Site assessments:															
IGA mod 2011	X	X	X	X	X	X	X	X	X	X	X	X	X	X	X
PASI	X	X	X	X	X	X	X	X	X	X	X	X	X	X	X
BSA	X	X	X	X	X	X	X	X	X	X	X	X	X	X	X
PRO assessments:															
NRS (pain, itching and scaling VAS)		X				X		X	X		X	X	X	X	X
DLQI		X				X		X	X		X	X	X	X	X
EQ-5D [®]		X				X		X	X		X	X	X	X	X
HAQ [®] -DI		X				X		X	X		X	X	X	X	X
TSQM		X				X		X	X		X	X	X	X	X
PBI		X				X		X	X		X	X	X	X	X
AE assessment (including injection site reactions)	X	X	X	X	X	X	X	X	X	X	X	X	X	X	X
Registration, drug supply, or completion	X ^e	X	X	X	X	X	X	X	X	X	X	X	X	X ^f	^e Registration only ^f Completion only

		Treatment Period 1							Treatment Period 2						
Period	Scr							EOT1					EOT2	Uns ^d	Comments
Visit	1	2	3	4	5	6	7	8	9 ^{a, b}	10	11	12	13	14 ^c	
Week	-4 to BL	BL	1	2	3	4	8	12	16	20	24	36	48	52	
Recommended visit window (days)		±2	±2	±2	±2	±5	±5	±5	±2	±5	±5	±5	±5	±5	

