6.5.2 Vital signs

Vital signs (including blood pressure and pulse measurements) will be assessed as indicated in [Table 6-1](#). After the patient has been sitting for 5 minutes, with back supported and both feet placed on the floor, **systolic blood pressure (SBP) and diastolic blood pressure (DBP) will be measured twice** (1 to 2 minutes apart) using a validated device with an appropriately sized cuff ([Mancia et al 2007](#)); each BP measurement will be recorded in the source. In case the cuff sizes available are not large enough for the patient's arm, a sphygmomanometer with an appropriately sized cuff may be used.

If possible, assessments should be performed per patient by the same study center staff member throughout the study.

Normal blood pressure will be defined as a SBP of 90 to < 120 mmHg, and a DBP of 60 to < 80 mmHg under the measurement conditions outlined above. Notable blood pressure will be hypertension (SBP of \geq 140 mmHg and/or DBP of \geq 90 mmHg) or hypotension (SBP of < 90 mmHg and/or a DBP of < 60 mmHg). A blood pressure indicative of pre-hypertension (SBP of 120 to < 140 mmHg and/or DBP of 80 to < 90 mmHg) will not be regarded as notable ([Chobanian et al 2003](#)).

A normal pulse rate will be defined as a rate of 60 to 100 beats per minute (bpm) under the measurement conditions outlined above. Notable pulse rates are a rate below 60 bpm (bradycardia) or above 100 bpm (tachycardia).

Whether action needs to be taken to address notable vital signs will be decided by the Investigator, taking into account the overall status of the patient. No specific action is foreseen as part of the study protocol.

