2.8.4.2 Vital signs

Vital signs (blood pressure, pulse rate, weight, waist circumference and hip circumference) will be summarized with standard descriptive statistics by visit, overall and by subpopulation presenting the baseline value, post-baseline value and change from baseline.

Newly occurring notable values for vital signs will be summarized. Notable values are defined as

- Systolic blood pressure (mmHg) ≥ 140 mmHg or < 90 mmHg
- Diastolic blood pressure (mmHg) ≥ 90 mmHg or < 60 mmHg
- Pulse (bpm) > 100 bpm or < 60 bpm

Data of subjects with newly occurring notable vital signs abnormalities will be listed in an additional listing.

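### SAP Table 2-1 gives vital signs the laboratory visit windows, which have no Week 8, so Week 8 blood pressure and pulse drop out of the by-visit summary or appear under another week

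*SAP*

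**What the plan says.** Protocol 6.5.2 ties vital signs to the assessment schedule: "Vital signs (including blood pressure and pulse measurements) will be assessed as indicated in" Table 6-1. In that table the vital-signs row is marked at screening, Baseline, Weeks 4, 8, 12, 16, 20, 24, 36, 48 and 52, and at unscheduled visits. The row headed "Laboratory sampling: safety panel (clinical chemistry, hematology, urine dipstick" has the same marks except at Week 8, where it is blank.

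SAP 2.1.1 says that windows apply to data summarized by visit, that they were built around each assessment's protocol visits, and that all visits are re-aligned into them. Table 2-1 assigns vital signs to column b: "b: laboratory sampling (Hematology, Chemistry and Urinalysis) and vital signs". The heading of that column covers assessments "scheduled at visits 2, 6, 8, 9, 10, 11, 12, 13 and 14", so Visit 7 is absent. Its Week 4 window is "Day 1 (post dose) – Day 57" and its Week 12 window is Day 58 to Day 99. When several quantitative values fall in one window, the one closest to the visit is kept, and the earlier one if they tie.

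SAP 2.8.4.2 applies this to the safety output: "Vital signs (blood pressure, pulse rate, weight, waist circumference and hip circumference) will be summarized with standard descriptive statistics by visit". Protocol 9.5.2 plans change-from-baseline summaries of vital signs at every post-baseline visit. SAP Section 4 declares one change from the protocol, concerning physical examinations, and does not mention Week 8 vital signs.

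**The concern.** Column b is right for the laboratory tests and wrong for vital signs, because the two schedules differ at Week 8. A patient who attends every visit on time has two scheduled vital-sign readings in one window, and the selection rule keeps one. The SAP foresees several values in a window only after major schedule deviations or unscheduled visits, so this looks like an oversight.

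There are two consequences. A planned safety time point cannot appear in the by-visit table. And where a Week 4 or Week 12 reading is missing, a reading taken about four weeks from that target fills its place under the wrong label. If the summary of newly notable vital signs is also built on windowed data, which the SAP does not say, Week 8 excursions would be lost there too.

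**Working it through.** Inputs:
- Target days (SAP Table 2-1): Week 4 = Day 29, Week 8 = Day 57, Week 12 = Day 85, Week 16 = Day 113.
- Protocol visit tolerance for Week 8 (Section 6 and Table 6-1): plus or minus "5 days for all other study visits".
- Tolerance for Weeks 4 and 12: at most 5 days. The Section 6 text lists Week 4 among the 2-day visits and Table 6-1 gives 5 days; the larger figure is used here.
- Window rule (SAP 2.1.1): for consecutive visits V_t and V_s an even number x of days apart, the upper limit for V_t is V_t + x/2 and the lower limit for V_s is V_s − x/2 + 1.

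Step 1, reproduce column b. Without Visit 7, Week 4 and Week 12 are consecutive, so x = 85 − 29 = 56. The Week 4 upper limit is 29 + 28 = 57 and the Week 12 lower limit is 85 − 28 + 1 = 58. Both match the SAP. The same rule reproduces all five columns of Table 2-1, so the arithmetic is sound; the fault is the visit list used for vital signs.

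Step 2, map an on-schedule Week 8 reading, Day 57 ± 5 = Day 52 to 62:

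| Day of Week 8 reading | Column b window | Distance from that window's target |
|---|---|---|
| 52 to 57 | Week 4 (target Day 29) | 52 − 29 = 23 to 57 − 29 = 28 days |
| 58 to 62 | Week 12 (target Day 85) | 85 − 58 = 27 down to 85 − 62 = 23 days |

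Step 3, apply the selection rule. An on-schedule Week 4 or Week 12 reading is at most 5 days from target and the Week 8 reading is at least 23 days from it, so the neighbour always wins. Any neighbour within 22 days of its target would also win. If the neighbour is missing, the Week 8 reading is kept and labelled Week 4 or Week 12. The nominal Day 57 is the last day of the Week 4 window, so attending one day late changes the reported week.

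Step 4, size. The planned post-baseline vital-sign visits are Weeks 4, 8, 12, 16, 20, 24, 36, 48 and 52, nine in all. One of nine is 11%. With 1,615 planned patients, at most 1,615 sets of blood pressure and pulse readings are involved.

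Step 5, apply the SAP rule to the protocol's own schedule:
- Week 4 to Week 8: x = 28, limits 29 + 14 = 43 and 57 − 14 + 1 = 44.
- Week 8 to Week 12: x = 28, limits 57 + 14 = 71 and 85 − 14 + 1 = 72.
- Week 12 to Week 16: x = 28, limits 99 and 100, as now.

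The windows become Week 4 = Day 1 (post dose) to 43, Week 8 = Day 44 to 71 and Week 12 = Day 72 to 99, with later windows unchanged. All of Day 52 to 62 then falls in Week 8.

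**The case against.** The case for leaving this as a minor correction has several parts.

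- The readings stay in the database, and the protocol plans listings of vital signs by patient and time. Windows apply only to by-visit data. This stands: the loss is from the by-visit summary, not from all reporting.
- The summary of newly notable values carries no by-visit wording, and the SAP defines post-baseline as all assessments after the first dose. That reading is plausible, so harm there is only possible. But the liver-test section states explicitly that abnormalities count at any time after baseline, and the vital-signs section does not, so clarification is worthwhile.
- Weight, waist and hip circumference, named in the same SAP paragraph, are in column f, are not scheduled at Week 8 and are unaffected. This stands.
- Gap-free windows accept distant values elsewhere: the Week 24 window in column b runs to Day 211, which is 211 − 169 = 42 days from target. True, but no vital-sign visit is scheduled between Weeks 24 and 36. Here a scheduled visit with its own target day is displaced.
- SAP 2.5.3 speaks of assigning windows for unscheduled visits, which might suggest that scheduled visits keep their eCRF label. That step concerns imputation of DLQI scores, and SAP 2.1.1 says all visits are re-aligned. Even on this reading, Table 2-1 offers no Week 8 slot for vital signs.
- The study is descriptive, safety rests mainly on adverse events, and Weeks 4 and 12 are still summarized. This limits the importance but does not make the table correct.

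**Conclusion.** The concern holds. As written, SAP Table 2-1 cannot produce a Week 8 row for blood pressure and pulse, although the protocol schedules the measurement and plans a summary at each post-baseline visit. One of nine post-baseline visits (11%) is lost from the by-visit summary, and some of its readings may appear under Week 4 or Week 12.

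This rests on two readings: that re-alignment covers scheduled visits, as SAP 2.1.1 states, and that closeness is measured from the nominal visit day. The 1,615 figure is a ceiling that assumes every planned patient attends Week 8; how often a neighbouring visit is missed cannot be estimated from the documents. The DLQI endpoint and the PASI and IGA responses use other columns that match their schedules and are not affected. The point should be corrected, but it does not threaten the main conclusions.

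**What to change.** Add a column to SAP Table 2-1 for blood pressure and pulse, covering Visits 2, 6, 7, 8, 9, 10, 11, 12, 13 and 14. Set Week 4 = Day 1 (post dose) to Day 43, Week 8 = Day 44 to Day 71 and Week 12 = Day 72 to Day 99, and leave later windows as they are. Restrict footnote b to laboratory sampling. Add one sentence to SAP 2.8.4.2 stating that newly occurring notable vital signs are derived from all post-baseline readings, scheduled or unscheduled, regardless of window.

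The cost is one table column, one sentence and the matching program change. No additional data are needed.
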